#### C. PRELIMINARY STUDIES

**Capacity of Research Team.** Completion of the proposed research will require experience with measuring cannabis withdrawal and gender-based substance use disorder research. As detailed below, the research team has the expertise to successfully complete the proposed work and a proven track-record in similar research areas.

**Experience with measuring cannabis withdrawal.** [name] (mentor) has conducted numerous NIH-funded studies with cannabis-dependent individuals that included regular assessment of cannabis withdrawal symptoms (K23DA15540; R21DA018221; R21DA022424; R01DA026782; R21DA034089). In a study of 87 cannabis-dependent individuals ([name] et al., 2011) craving responses to marijuana cues was assessed using the marijuana craving questionnaire (MCQ) and exposure to the cues produced a significant increase in the MCQ total score (p=0.005). Additional clinical trials assessing buspirone for cannabis dependence ([name] et al., 2015), vilazodone for cannabis dependence ([name] et al., 2016), and the effect of oxytocin on craving and stress response in cannabis-dependence all included assessments of cannabis withdrawal. [name] recently completed a pilot study examining a cognitive bias modification paradigm on cue-reactivity in cannabis-dependent adults which also included assessment of withdrawal symptoms (under review). These studies demonstrate the team's ability to assess cannabis withdrawal in cannabis dependent adults.

**Experience with gender-based research.** Drs. [name] and [name] have conducted numerous gender-based studies in substance-abusing populations including as part of the Specialized Center of Research (SCOR) on Sex/Gender Factors Affecting Women's Health (P50 DA016511-14). In recent studies [name] has examined baseline gender differences among treatment seeking cannabis-dependent adults ([name] et al., 2017), which included important findings on withdrawal symptoms, as well as a study on motivation for change and cannabis outcomes in a pharmacotherapy trial ([name] et al., 2016). In addition, recently completed gender-based studies include a gender-based investigation of yohimbine and drug cues on impulsivity in cocaine users (Moran-Santa Maria, Baker, [name], et al., 2016), and a review of menstrual phase cycle research with recommendations for assessment and future research (Allen, [name], et al., 2016).

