Adherence Monitoring. Participants will record themselves taking their morning and evening medication doses and then submit these videos to research staff via RedCap survey. Subjects may use their personal smartphones for video submission. If they do not have a smartphone, one will be loaned to them during the course of the study, as video submissions may only be completed on a smartphone (cannot be completed on a computer). A survey link will be sent to the subject via text message twice daily. Video capture will occur as part of the RedCap survey. Videos are automatically stored on some Android smartphones, and participants will be informed of that so they can delete the files, if necessary. Participants using iPhones (and using loaner iPhones from our group) will not have stored videos on their phone and nothing will need to be deleted.

**Ovarian Hormones:** *Progesterone* and *Estradiol* will be measured from salivary samples collected using the passive drool method. Saliva samples will be collected daily; in the lab on days 1 and 5, and at home on days 2-4. Participants will be trained on how to collect and store the samples by study personnel on study day 1.

**Cannabis Withdrawal.** The *Cannabis Withdrawal Scale (CWS; Allsop et al., 2011)* will be used to assess cannabis withdrawal symptoms. CWS is a 19-item self-report measure that assesses cannabis withdrawal symptoms in the past 24 hours (sample items: I felt restless; I had a headache; I had trouble getting to sleep at night) on a 10-point Likert scale (0=Not at All to 10=Extremely). To establish a baseline withdrawal score, the CWS will be administered in person on study day 1. CWS will then be administered once on study days 1 and 5, and twice daily on study days 2-4 as part of the RedCap medication adherence survey that will be sent via text message to the participant. Participants will be asked to respond with reference to the past 12 hours.

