**Cannabis Abstinence.** Cannabis abstinence will be assessed using self-report, saliva drug testing, and cannabinoid levels. Self-report will be conducted using the TLFB (see *Instrumentation* section). Saliva drug testing will occur in person on Days 1 and 5, and participants will be trained to administer saliva screening. During days 2-4, participants will schedule a Skype/FaceTime call with study personnel and undergo drug screen procedures via teleconference. Cannabinoid levels will be assessed using urine toxicology collected on Days 1 and 5. Creatinine-corrected cannabinoid levels will be compared from Day 1 to Day 5 to confirm abstinence during the study period.

**Cognitive Testing.** The Symbol Digit Modalities Test (SDMT; Smith, 1982), Go/NoGo Inhibitory Control (IC) Task (Chikazoe et al., 2009), and Approach-Avoidance Task (Wiers et al., 2009) will be used to assess cognitive functioning. The SDMT measures sustained attention, response speed, and visuomotor coordination. It involves filling in a blank space below a symbol with the appropriate symbol-paired number as quickly as possible for 90 seconds. The main outcome is number of correct responses. A computerized IC task will be used to assess response inhibition. During the IC task, participants are instructed to press a button in response to common (75% of trials) and rare (12.5%) Go stimuli while inhibiting responding to rare NoGo stimuli (12.5%). The task provides errors of omission and reaction times during Go trials, and errors of commission on NoGo trials, and has been used in substance abusing populations (Froeliger et al., 2017). The AAT will be used to assess cannabis approach bias – a measure of implicit cognitive bias towards cannabis cues. During the AAT, participants are asked to respond to cannabis-related or neutral images by pushing or pulling a joystick based on an irrelevant image feature (i.e. border color). Primary outcome is cannabis approach bias, and a higher score indicates greater bias.

**Nicotine Dependence**: The *Fagerstrom Test for Nicotine Dependence (FTND; Heatherton, et al., 1991)* will be administered at screening to inform randomization procedures.

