**Consent and Screening Interview.** Potential participants will present to the Addiction Sciences Division (ASD) Research Clinic and will be given a full description of the study procedures and asked to read and sign an IRB-approved informed consent form. The Mini-International Neuropsychiatric Interview (M.I.N.I.; Sheehan et al., 1998) will assess exclusionary psychiatric and substance use diagnoses during the past year, including frequency of cannabis use. Participants will provide a urine sample, which will first be tested for pregnancy and subsequently for substance use. Past month cannabis and all other substance use will be assessed using the Timeline Follow-Back (TLFB; Sobell & Sobell, 1992). A medical history and physical exam will be conducted to ensure that the individual is eligible to participate. Participants will provide expected date of menses onset for study personnel to follow-up prior to study day 1 visit.

**Tracking period between screening and study day 1 visit:** Following screening visit participants will be asked to track their menstrual cycle and contact the clinic upon menses onset. Study personnel will reach out to participants 3 days prior to expected onset provided at screening as a reminder. Upon menses onset, participants will schedule study day 1 visit to occur within 3 days, or on Monday if onset occurs on the weekend (Friday-Sunday). *Study day 1 must occur on Monday, Thursday, or Friday in order to assure in-person visit on study day 5.* Participants will be asked to begin abstinence on Study Day 1.

**Study day 1 visit:** Participants will present to ASD and undergo urine toxicology, Breathalyzer, saliva testing, and TLFB. After all inclusion criteria and no exclusion criteria have been satisfied, the participant will be randomized to either the experimental (progesterone 200mg bid) or control (placebo) condition based on nicotine dependent status (FTND score of 4 or greater, versus 3 or below). Participants will then provide a saliva sample for progesterone and estradiol quantification, followed by cognitive testing, and then self-report assessments (see *Instrumentation* section). Participants will then receive medication instructions and review medication adherence procedures (see *Adherence* section). Participants will be instructed to take first dose of medication at 9:00pm that evening to minimize sedation. Participants will then be compensated and discharged.

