#### Example study day 1 timeline

Time	Procedure	Duration
9:00 am	Saliva, breathalyzer, utox	15 mins
9:15	TLFB	15 mins
9:30	Saliva sample (hormones)	5 mins
9:35	Cognitive testing	15 mins
9:50	Self-report assessments (FrSBe, CWS, PANAS-X, CUDIT-R)	20 mins
10:10	Medication instructions	20 mins
10:30	Compensate/discharge	
9:00 pm	First medication dose, CWS (at home)	

**Study days 2-4:** Participants will be prompted by RedCap to complete medication adherence and CWS at 9am and 9pm. Each day participants will schedule a Skype/FaceTime call with study personnel to conduct saliva testing and adverse event assessment. Should an adverse event occur, trained personnel will assess via video conference to determine necessary procedures. Participants will also provide a saliva sample for hormone testing. Participants will be provided with labeled tubes for saliva collection and storage. They will fill out the date and time and place in the freezer to be stored until study day 5 when they will bring to ASD clinic for testing.

**Study day 5 visit:** Participants will present to the ASD clinic by 10am for final study visit. They will undergo saliva testing, urine toxicology, Breathalyzer, and TLFB, followed by hormone saliva sampling and cognitive testing. Participants will be debriefed, compensated, and discharged.

Time	Procedure	Duration
9:00am	Last medication dose, CWS (at home)	
9:00	Saliva, breathalyzer, utox	15 mins
9:15	TLFB	15 mins
9:30	Saliva sample (hormones)	5 mins
9:35	Cognitive testing, FrSBe	15 mins
9:50	Compensate/debrief	10 mins
10:00	Discharge	

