## c. Potential Risks

- 1. Risks due to micronized progesterone: Micronized progesterone is generally well tolerated. The most common adverse effect is sedation. Other less common adverse effects include menstrual irregularity, spotting or breakthrough bleeding, dizziness, cramps, nausea, fatigue, headache and breast tenderness (de Lignieres, 1999; Simon, 1995). Other side effects attributed to synthetic progesterone, including depression, fluid retention, pruritus, jaundice, rash and thrombotic disorders, are unlikely to occur. Recently there has been reports of increased risk of stroke, coronary artery disease, venous thromboembolism and breast cancer in postmenapousal women who have been on long-term hormone replacement treatment with estradiol and progestin (medroxyprogesterone) combination (Grady et al., 2002; Hulley et al., 2002; Nelson et al., 2002). While some of these adverse events develop after years of treatment, venous thromboembolism is seen within the first year of treatment (2002b). It is possible that progestins may contribute to thromboembolism seen during estradiol and progestin treatment and thromboembolism is listed in the PDR as one of the adverse events for medroxyprogesterone treatment (PDR, 2002). In contrast to synthetic progestins, progesterone is not known to cause thromboembolism (PDR, 2002).
- 2. Risks due to study procedures: Participants will be asked not to smoke cannabis for 5 days. During this cannabis abstinence period, participants may experience symptoms of cannabis withdrawal such as craving cannabis, mild anxiety, insomnia, irritability, restlessness, stomachache, headache, nausea, loss of energy or appetite, chills, diaphoresis, and feeling depressed.
- 3. Potential risks of rating scales and questionnaires: These are all non-invasive, should add no risk, and have been used without difficulty or any adverse events in our previous studies with this population. The only minor inconvenience could be the time taken to complete them. Some participants may feel uncomfortable disclosing personal thoughts and feelings. Careful efforts aimed at maintaining confidentiality have been effective in previous research, and only participants' code numbers will be recorded on the forms themselves to protect confidentiality.

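### The day 1 baseline CWS follows a battery with cannabis images, which may slightly raise it; giving the CWS first costs nothing

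*Combined protocol and SAP*

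**What the plan says.** Section D2 (Cannabis Withdrawal) defines the reference score: "To establish a baseline withdrawal score, the CWS will be administered in person on study day 1". The follow-up schedule is then: "CWS will then be administered once on study days 1 and 5, and twice daily on study days 2-4".

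For the day 1 clinic visit, section D2 (Study day 1 visit) places the hormone saliva sample first, "followed by cognitive testing, and then self-report assessments". The Example study day 1 timeline agrees. Cognitive testing starts at 9:35 and lasts 15 minutes. At 9:50 comes a 20-minute block listed as "Self-report assessments (FrSBe, CWS, PANAS-X, CUDIT-R").

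The cognitive battery has three tasks. In one of them, the AAT, "participants are asked to respond to cannabis-related or neutral images by pushing or pulling a joystick". The order of the three tasks is not stated.

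On day 5 the order is reversed. The example timeline has the CWS at home at 9:00 with the last dose, and cognitive testing at 9:35.

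Two other places bear on this. Section C says of the team's earlier study of 87 cannabis-dependent people that "exposure to the cues produced a significant increase in the MCQ total score (p=0.005"). Section E (Potential Risks) says that during abstinence "participants may experience symptoms of cannabis withdrawal such as craving cannabis, mild anxiety, insomnia, irritability", among other symptoms.

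**The concern.** The baseline CWS is taken within minutes of exposure to cannabis images, and no later CWS is taken in that situation. The documents supply both links that make this matter: cues raised craving in this team's own work, and craving is named as a withdrawal symptom. If the images lift some CWS answers, the baseline sits higher than it would in the conditions under which follow-up is measured.

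Two things could then suffer. First, the within-arm rise from baseline, which is how a pilot of this kind shows that abstinence produced withdrawal, would look smaller than it was. Second, women differ in how they react to cues, so the baseline would carry extra noise and be less useful in a change score or as a covariate. Withdrawal symptoms are a primary outcome (section D1, Study Overview), and the in-person day 1 score is the only one designated as baseline, so it cannot be retaken later.

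**Working it through.** The documents give no SD, effect size, alpha or power for the CWS, so there is no stated figure to reproduce. The check is of timing, then of consequences under stated assumptions.

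**1. Timing** (section D2 and the two example timelines)

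| CWS | Place and time | Relation to an AAT |
|---|---|---|
| Baseline, day 1 | clinic, in the 9:50 block | battery 9:35 to 9:50, same morning |
| Day 1 evening | home, 9pm | battery ended 11 h 10 min earlier (21:00 − 9:50) |
| Days 2-4 | home, 9am and 9pm | none since day 1 |
| Day 5 | home, 9am | 35 min before that day's battery (9:35 − 9:00) |

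Administrations after baseline: 1 + (3 × 2) + 1 = 8. None directly follows an AAT. The baseline block opens 0 to 15 minutes after the AAT, depending on the unstated task order, plus the time for the FrSBe if the listed order is kept.

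**2. What the cue evidence gives.** If p=0.005 in 87 people came from a simple pre/post test (an assumption), t is about 2.88 and the standardised effect is 2.88/√87 = 0.31 SD of change. That is change in MCQ craving. Nothing in the documents converts it to CWS points.

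**3. Possible size on the CWS.** Section D2 gives 19 items scored 0 to 10, so the maximum is 19 × 10 = 190. Assume 1 to 3 items rise by 1 to 3 points each:
- smallest: 1 × 1 = 1 point (1/190 = 0.5%);
- largest: 3 × 3 = 9 points (9/190 = 4.7%).

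The recall period works against the larger values. The 15-minute battery is 15/720 = 2.1% of a 12-hour window and 15/1440 = 1.0% of a 24-hour window.

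**4. Within-arm rise.** Observed rise = true rise − shift. With an assumed placebo rise of 15 points, a 4-point shift leaves 15 − 4 = 11, and a 9-point shift leaves 15 − 9 = 6.

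**5. Arm contrast.** A shift common to both arms cancels in a difference of change scores and is absorbed by the intercept in a baseline-adjusted model. This was simulated with 20,000 runs and 20 per arm. Every other input is an assumption: baseline mean 30, SD 20, placebo rise 15, treatment effect −12, pre-post correlation 0.5 (residual SD 17.3).

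| Baseline shift, mean (SD) | Change score: effect, power | Baseline-adjusted: effect, power |
|---|---|---|
| 0 (0) | −12.0, 0.46 | −11.9, 0.56 |
| 4 (0) | −12.0, 0.45 | −12.0, 0.56 |
| 9 (0) | −11.9, 0.45 | −12.0, 0.56 |
| 4 (4) | −12.1, 0.45 | −12.0, 0.56 |
| 9 (9) | −12.1, 0.40 | −12.0, 0.54 |

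The effect estimate stays at −12 throughout. The small power differences in the uniform-shift rows are simulation error.

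**6. Why power moves only when reactions vary.** Variance of the change score: 0.5² × 20² + 17.3² = 100 + 299 = 399, SD 20.0. Adding reactivity with SD 9 gives 399 + 81 = 480, SD 21.9. For the baseline-adjusted model, residual variance goes from 299 (SD 17.3) to 399 − 200²/(400 + 81) = 399 − 83 = 316 (SD 17.8).

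**The case against.** The strongest reply is that no effect on the CWS is shown. The cue result in section C concerns MCQ craving after cues whose type is not given. The AAT asks for a joystick response to an irrelevant image feature. The CWS is a retrospective report over 12 or 24 hours, and the sample items quoted are restlessness, headache and trouble sleeping; no craving item is quoted. All of this stands. It limits the point to a plausible effect of unknown and probably small size.

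Second, Aim 2 compares progesterone with placebo. The plan specifies no test of the within-arm rise and calls all its analyses preliminary. This also stands, and it is why the severity is minor. The plan does not say how baseline CWS enters the mixed model, so the somewhat larger precision loss of a change score cannot be ruled out.

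Third, a reader might infer that no follow-up CWS is touched by the AAT at all. That goes too far: the 12-hour window of the 9pm CWS on day 1 runs from 9am and includes the 9:35 battery. Only the direct sequence is unique to baseline.

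Fourth, moving all the questionnaires ahead of the battery would do harm. PANAS-X and CUDIT-R are not given on day 5, and the FrSBe is listed there with cognitive testing, so the run-up to cognitive testing would then differ between the two visits. This is correct, and the change below moves the CWS only.

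Finally, reordering does not equalise everything. The Timeline Follow-Back interview about cannabis use at 9:15 would still come before the day 1 CWS, the clinic and home settings differ, and it is unclear whether the 12-hour recall instruction applies to baseline. These differences remain; they are no reason to keep the one that can be removed by reordering.

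**Conclusion.** The mismatch in order is real: baseline CWS follows the cannabis-image battery within minutes, no later CWS directly follows an AAT, and day 5 uses the opposite order without a stated reason. The consequence is only possible. Baseline may be slightly raised and noisier, and the within-arm rise understated by the same number of points. The range of 1 to 9 points of 190 rests wholly on the assumption about how many items move and by how much.

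A reader might infer that baseline is inflated as a matter of fact, or that the treatment comparison is biased. The documents support neither. The first would need evidence of an AAT effect on the CWS, and none is given. The second fails because both arms go through the same sequence before the first dose at 9pm, assuming participants do not know their allocation at that point. Even at the upper end of the assumed range, with reactions varying widely between women, simulated power falls only from 0.46 to 0.40 for a change score, or from 0.56 to 0.54 with baseline adjustment.

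This is a free improvement of minor severity.

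**What to change.** In section D2 (Study day 1 visit) and the Example study day 1 timeline, give the CWS on its own after the hormone saliva sample and before cognitive testing. This matches day 5, where the CWS already precedes the battery.

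State the order of the three cognitive tasks and place the AAT last at both visits, so that cannabis images do not precede the other two tasks. The two changes belong together: with the CWS left where it is, an AAT placed last would bring the images closer to it.

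Leave FrSBe, PANAS-X and CUDIT-R after the battery on day 1, so that the questionnaires completed before cognitive testing are the same on days 1 and 5.

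The cost is a wording change in the visit description, the timelines and the cognitive testing paragraph. No visit, instrument or time is added: the cognitive and self-report blocks still total 15 + 20 = 35 minutes. The change is best made before the first participant, because a later switch would leave women with baselines taken under two different orders.

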#### Example study day 1 timeline

Time	Procedure	Duration
9:00 am	Saliva, breathalyzer, utox	15 mins
9:15	TLFB	15 mins
9:30	Saliva sample (hormones)	5 mins
9:35	Cognitive testing	15 mins
9:50	Self-report assessments (FrSBe, CWS, PANAS-X, CUDIT-R)	20 mins
10:10	Medication instructions	20 mins
10:30	Compensate/discharge	
9:00 pm	First medication dose, CWS (at home)	

**Study days 2-4:** Participants will be prompted by RedCap to complete medication adherence and CWS at 9am and 9pm. Each day participants will schedule a Skype/FaceTime call with study personnel to conduct saliva testing and adverse event assessment. Should an adverse event occur, trained personnel will assess via video conference to determine necessary procedures. Participants will also provide a saliva sample for hormone testing. Participants will be provided with labeled tubes for saliva collection and storage. They will fill out the date and time and place in the freezer to be stored until study day 5 when they will bring to ASD clinic for testing.

**Study day 5 visit:** Participants will present to the ASD clinic by 10am for final study visit. They will undergo saliva testing, urine toxicology, Breathalyzer, and TLFB, followed by hormone saliva sampling and cognitive testing. Participants will be debriefed, compensated, and discharged.

Time	Procedure	Duration
9:00am	Last medication dose, CWS (at home)	
9:00	Saliva, breathalyzer, utox	15 mins
9:15	TLFB	15 mins
9:30	Saliva sample (hormones)	5 mins
9:35	Cognitive testing, FrSBe	15 mins
9:50	Compensate/debrief	10 mins
10:00	Discharge	

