#### D. RESEARCH DESIGN AND METHODS

#### **D1. General Procedures:**

**Study Overview.** The proposed study will investigate the effect of exogenous progesterone on cannabis withdrawal among female cannabis users. Forty heavy-cannabis-using women will be randomized based on nicotine dependent status to receive placebo or progesterone (200mg bid) over a consecutive 5-day period during the early follicular phase of their menstrual cycle and asked to abstain from cannabis. Menstrual phase will be determined by onset of menses and ovarian hormone levels. Following screening, within 3 days of onset of menses, participants will undergo study visit 1 (day 1 abstinence) which includes biochemical, subjective, and cognitive performance assessments, randomization, and medication instructions; they will take their first medication dose that evening. Participants undergo study procedures on study days 2-4 at home and will return to the clinic on study day 5 for repeat assessments. Salivary progesterone and estradiol levels will be collected daily, and cannabis withdrawal will be assessed twice daily, concurrent with medication adherence procedures. Primary outcomes include progesterone levels and cannabis withdrawal symptoms.

**Recruitment.** Women who use cannabis daily or near daily will be recruited from the community based on previously successful techniques used over the past 20 years by the research team. This will include a mix of community, print, and online advertising.

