## **D2. Participant Procedures:**

**Medication administration and adherence monitoring.** *Micronized progesterone (Prometrium; 200mg)*: Progesterone is a hormone released mainly during the luteal phase of the menstrual cycle and pregnancy, and has been used for over 50 years in the treatment of various disorders including ovarian failure, premenstrual symptoms, amenorrhea, dysfunctional uterine bleeding, menopausal symptoms and for contraception (de Lignieres, 1999; Simon, 1995). Because it is poorly absorbed and has extensive first pass metabolism, several synthetic progesterone derivatives have been synthesized and marketed. However, these synthetic progesterone derivatives have additional androgenic, corticosteroid and anabolic effects and have been associated with unfavorable side effects including fluid retention, androgenic effects and alterations in lipid profile (Goodman et al., 1996). Recently, micronized progesterone formulations that can be taken orally have been developed to overcome the poor absorption of progesterone and the unfavorable side effects of the synthetic progesterone (McAuley et al., 1996; Simon, 1995). The safety, tolerability and efficacy of micronized progesterone and subjective measures have been investigated over a wide dose range, from 200 to 2,000 mg/day (Freeman et al., 1995; Gron et al., 1997; Schweizer et al., 1995). Micronized progesterone provides a specific pharmacological tool to investigate the effects of this hormone, devoid of the additional pharmacological effects that synthetic progesterone derivatives have.

Progesterone or placebo dosing will begin at 9pm on study day 1. On study days 2-4 participants will take medication at home at 9am and 9pm, and on day 5 the final dose will be taken at 9am. Capsules will be prepared by the MUSC Investigational Drug Services. Previous studies (Fox et al., 2013; Sofuoglu et al., 2001; 2011) have used twice daily administration during the follicular phase of 200mg progesterone in order to achieve stable levels of progesterone comparable to normal luteal phase levels (2-20 ng/ml). Safety and tolerability of micronized progesterone has been established in numerous studies with nicotine (Sofuoglu et al., 2001; 2011) and cocaine (Evans & Foltin, 2006; Fox et al., 2013; Reed et al., 2011 Sofuoglu et al., 2002; 2004) dependent individuals.

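### The Day 1 9pm withdrawal score is taken with the first dose but is left among the follow-up measures; an arm effect averaged over them would shrink to 7/8

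*Combined protocol and SAP*

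**What the plan says.** Withdrawal is a primary outcome. Section D1 (Study Overview) states: "Primary outcomes include progesterone levels and cannabis withdrawal symptoms". The same section says that "cannabis withdrawal will be assessed twice daily, concurrent with medication adherence procedures".

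Section D2 (Cannabis Withdrawal) fixes the baseline: "To establish a baseline withdrawal score, the CWS will be administered in person on study day 1". In the example timeline this falls in the self-report block at 9:50 am. D2 continues: "CWS will then be administered once on study days 1 and 5, and twice daily on study days 2-4", through the text-message adherence survey. On the recall window it says: "Participants will be asked to respond with reference to the past 12 hours".

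On dosing, D2 states: "Progesterone or placebo dosing will begin at 9pm on study day 1". The example Day 1 timeline puts two things on one line at 9:00 pm: "First medication dose, CWS (at home").

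The Statistical Analyses section tests all hypotheses with a random-effects mixed model for repeated measures, with a random intercept per woman. It does not list the CWS time points that are outcomes. It also does not say how baseline enters the model, or whether the test is an arm main effect, an arm-by-time term or a contrast at Day 5.

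**The concern.** The 9pm score on Day 1 comes after randomization and after the named baseline, yet it describes a period in which nobody has taken study medication. Its expected arm difference is zero whatever progesterone does.

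The only baseline split in the plan places this score with the later measures. An analyst who takes the in-person score as baseline and everything after it as outcome would include it. With a random intercept, an arm main effect and complete data, the arm estimate is the difference in simple means over all outcome scores, so this score would get the same weight as the exposed ones.

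The result would be an efficacy estimate pulled toward no effect. The sample of 40 is described as the most that can be attained, so the loss could not be recovered by enrolling more women. The trial is also meant to inform a larger study.

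**Working it through.** **1. Count the scores.** From D2, the scores after the named baseline are 1 (Day 1, 9pm) + 3 x 2 (Days 2-4) + 1 (Day 5, 9am) = 8. The compensation table agrees: the medication/CWS row is 20 + 40 + 40 + 40 + 20 = 160 dollars, and 160 / 20 dollars per completion = 8.

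**2. Classify them.** The first dose is at 9pm on Day 1. A 12-hour window ending then runs from about 9am to 9pm and is wholly pre-dose. The 24-hour window that D2 gives when describing the scale would be pre-dose as well. The first score with any exposure is Day 2, 9am. So 1 of the 8 scores is unexposed and 7 are exposed.

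**3. Size of the estimate.** Let the arm differences at the 7 on-dose scores have mean D. Averaged over 8 scores, the expected difference is (0 + 7D) / 8 = 0.875D, which is 12.5% smaller. This does not depend on the shape of the effect. A linear build-up to a full effect of 1 averages 0.500 over 8 scores and 0.571 over 7, and 0.500 / 0.571 = 0.875.

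**4. Information.** Assume a constant on-dose effect, equal correlation rho between scores and no missing data. The documents give no rho. The variance of a woman's mean over m scores is proportional to v(m) = (1 + (m - 1)rho) / m. The information from 8 scores relative to 7 is 0.875² x v(7) / v(8):

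| rho | v(7) | v(8) | ratio | equivalent of 40 women |
|---|---|---|---|---|
| 0.4 | 0.4857 | 0.4750 | 0.783 | 31.3 |
| 0.6 | 0.6571 | 0.6500 | 0.774 | 31.0 |
| 0.8 | 0.8286 | 0.8250 | 0.769 | 30.8 |

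Adjusting for the in-person baseline subtracts rho² from both variances and changes little. At rho 0.4 the ratio is 0.7656 x 0.3257 / 0.3150 = 0.79. At rho 0.8 it is 0.7656 x 0.1886 / 0.1850 = 0.78.

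**5. Illustrative power.** The plan's sample size cannot be reproduced, because it states no effect size, SD, alpha or power. The table assumes 20 per arm, two-sided alpha 0.05, a true effect of 0.5 SD at every on-dose score and the normal approximation (slightly optimistic at this size):

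| rho | 8 scores, unadjusted | 7 scores, unadjusted | 8 scores, baseline-adjusted | 7 scores, baseline-adjusted | 7 scores, both pre-dose scores as covariates |
|---|---|---|---|---|---|
| 0.3 | 0.60 | 0.71 | 0.72 | 0.81 | 0.87 |
| 0.5 | 0.45 | 0.55 | 0.70 | 0.80 | 0.90 |
| 0.7 | 0.36 | 0.45 | 0.79 | 0.88 | 0.97 |
| 0.8 | 0.33 | 0.41 | 0.90 | 0.95 | 0.996 |

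The last column uses v = (1 + 6rho)/7 - 2rho²/(1 + rho). It depends most on equal correlation, because it treats the 9pm score as being as predictive as any other.

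**6. Other contrasts.** A Day 5 contrast gives the 9pm score no direct weight in the effect. In a group-by-time test, the score serves as a pre-dose anchor. If the effect were constant from Day 2 9am, an arm-by-time slope fitted to the 7 on-dose scores alone would have zero expected signal, and the Day 1 scores would supply it. The dilution in steps 3 and 4 therefore belongs to the averaged contrast only.

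**The case against.** The strongest reply is that the plan never says the 9pm score is an outcome. D2 sets out a schedule, not an analysis rule, and Statistical Analyses names no contrast. The hypothesis speaks of reductions in symptoms, which can be read as change over time, and in that test the score helps. This stands. A reader might infer that the plan counts the score as follow-up and so dilutes its primary effect, but the documents support only a conditional statement.

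Two further inferences also go too far. One is that the in-person score would be an outcome too, making 2 of 9 scores unexposed; D2 expressly calls that score the baseline. The other is that the 9pm score is a better pre-treatment value than the clinic score. A daytime window suits the sleep items poorly. How far the clinic score reflects ongoing use is also unsettled: D2 starts abstinence on Day 1, while the drug-screening text in D3 speaks of establishing abstinence before study procedures. The 9pm score is best treated as an additional pre-dose value, not a replacement.

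It can also be said that one score in eight, in a pilot whose analyses are called preliminary, is a small matter. That limits the severity, but the correction costs almost nothing.

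**Conclusion.** The concern holds in conditional form. The Day 1 9pm score cannot show a drug effect, the plan's only baseline split leaves it among the later measures, and the analysis section does not remove it. If Hypothesis 2 is tested as an arm difference averaged over all 8 scores, the expected estimate is 7/8 of the mean on-dose effect. Information is then about 77-78% of what the 7 on-dose scores give, roughly 31 of 40 women. The 7/8 rests on equal weighting. The information figure also rests on a constant effect, equal correlation of 0.4 to 0.8 and complete data, none of which the documents supply. The bias is toward no effect. A Day 5 or group-by-time contrast is not diluted in this way.

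A reader might also see a dosing contradiction, because D1 describes twice-daily dosing "over a consecutive 5-day period" while the D2 schedule gives 1 + 6 + 1 = 8 doses from the evening of Day 1 to the morning of Day 5. Those doses do fall on five consecutive calendar days, and D1 itself has the first dose in the evening. At most the two descriptions should be reconciled; nothing in this point depends on it.

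**What to change.** In D2 (Cannabis Withdrawal) and in Statistical Analyses:

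- Classify both Day 1 CWS scores as pre-dose.
- Define the test of Hypothesis 2 as the arm difference averaged over the 7 scores from Day 2 9am to Day 5 9am.
- Adjust for the in-person baseline and, as a further pre-dose value, the Day 1 9pm score.
- Place the CWS before the capsule step in the Day 1 evening survey. The score follows randomization, so its use as a covariate requires that it precede the dose and that women do not know their arm.

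The cost is wording and one change of item order. There are two downsides. The contrast has one fewer outcome score. In addition, a woman who misses the Day 1 evening survey would drop out of a standard covariate-adjusted model, which would undercut the plan's reliance on a model that tolerates partly missing data. State the handling in advance: for example, model the pre-dose scores jointly with the outcomes with the arms constrained equal before dosing, or impute the missing covariate.
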